6. TRIAL PROCEDURES

6.1 Screening Assessments

All subjects will receive a written consent form and a verbal explanation of the study by an investigator and/or the research study coordinator and will be asked to sign the written informed consent. Study participants will have the presence of inclusion criteria (section 4.1) and absence of exclusion criteria (section 4.2) verified by providing a comprehensive medical history (and a urine pregnancy test in the case of women of child bearing potential).

6.2 Treatment Administration

Administration of Definity will be performed under direct supervision of a medical doctor. Emergency services (e.g., a crash cart) will be available within the hospital in case of any acute adverse reactions. Additionally, resuscitation equipment and trained CPR personnel will be in immediate proximity to the patient during Definity administration.

Briefly, Definity microbubbles will be activated with a Vialmix device using a full 45-second activation cycle to ensure consistent microbubble size, as per manufacturer's recommendation. A needle will be

inserted into an activated Definity vial to be used as an air vent. An 18 to 20 gauge needle will be attached to 3 or 5 cc syringe and inserted into the vial to withdraw 1.3 to 1.5 ml of activated Definity. All subjects will receive an initial bolus injection at a steady rate not to exceed 1 ml/s with doses of 1.3 to 1.5 ml. Each bolus injection of Definity will be followed with a flush of 10 ml of normal saline. Following a 15 minutes interval a dose of one vial of activated Definity, mixed in 25 ml of saline, will be prepared for each subject and infused through a peripheral vein at a rate sufficient to provide diagnostic intra-tumoral contrast visibility. Infusions will be performed as described in the “Instructions for Use” provided by the manufacturer. All materials and supplies used for the infusion procedure will be identical to those described by the manufacturer. Up to 1.5 ml of activated Definity per vial will be extracted (as described above) and added to 25 ml of preservative-free saline. The IV bag will then be gently squeezed to evenly distribute the microbubbles and an infusion will be initiated. As per the manufacturer’s recommendation the infusion rate may vary between 4 ml/min to 10 ml/min and in this study the infusion rate will be maintained within this range but will be adjusted to provide diagnostic intra-tumoral contrast visibility.

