Prior to a subject undergoing surgery of an adnexal mass, a baseline grayscale scan of the lesion will be obtained, while power Doppler imaging (PDI) will be performed to select the area with the greatest vascularity. Two contrast injections will be administered. The first injection will involve pulse inversion grayscale EV SHI of the area of greatest vascularity within the adnexal mass (established by baseline PDI). There will be a 15 minute pause between injections to allow for complete contrast clearance. For the second injection, Definity will be infused over 5 minutes and subharmonic destruction/reperfusion SHI imaging performed in multiple imaging planes covering the adnexal mass.

The pre- and then post-contrast US imaging will be read independently by the 2 experienced co-investigators blinded to the surgical results and contrast-enhanced MRI evaluations. Then, sensitivity, specificity and accuracy will be calculated for all imaging modalities (baseline and SHI as well as MRI) and compared to the RMI used to select patients for surgery [Ferrazzi et al. 1997; 2005; Moolthiya & Yuenyao 2009]. Off-line SHI time intensity curves (TICs) will be created on a pixel by pixel basis and TIC parameters will be compared to the lesion characterization by the other imaging modalities with pathology as the reference standard. Finally, the ability of EV SHI to image angiogenesis (specifically fractional tumor vascularity) will be compared to so called “hot spots” within surgical specimens stained for an immunohistochemical predictor of angiogenesis (the endothelial cell marker CD31).

Statistical Methodology: As this project involves a pilot study of a new US imaging mode (SHI) in a completely new application, no power analysis can be performed *a priori*. Nonetheless, our statistical analysis will address the following two major questions:

1. Can EV SHI biomarkers improve the characterization of benign and malignant adnexal masses compared to standard US or contrast enhanced MRI or other parameters?
2. Do SHI ovarian neovascularity measurements correlate with iMVD as a marker of angiogenesis?

As a pilot study this project is not powered to provide definitive answers to the questions presented above, but rather is a first step towards establishing feasibility and to provide data for a future more exhaustive study.

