Briefly, Definity will be administered by bolus IV injection through an 18 to 20 gauge angiocatheter placed in a peripheral arm vein, preferably an antecubital vein. Subjects will be instructed not to move their arm during the administration of the contrast agent. All subjects will receive an initial bolus injection at a steady rate not to exceed 1 ml/s with doses of 1.3 to 1.5 ml. Each bolus injection of Definity will be followed with a flush of 10 ml of normal saline. There will be a 15 minute pause between injections to allow for complete contrast clearance. For the second injection, we will infuse up to 1.5 ml of Definity mixed in 25 ml of saline over 5 minutes (which is the approved dose and concentration for infusion of Definity).

Definity will be stored in a secure cabinet, with only the study investigators and research personnel having access. New vials must be prepared for each subject's contrast administration. Unused drug and empty vials will be properly disposed of after reconciling in the log of study drug.

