Two contrast injections will be performed. The first injection will involve pulse inversion grayscale EV SHI (in a dual display format utilizing at a transmit frequency of 5.8 MHz and the subharmonic obtained at 2.9 MHz [Eisenbrey et al. 2011a; Sridharan et al. 2015]) of the area of greatest vascularity within the adnexal mass (as established by baseline PDI) followed by IV administration of 1.3 to 1.5 ml of Definity and acquisition of the contrast enhancement covering baseline, wash-in and peak enhancement to complete wash-out (typically 1-2 minutes). There will be a 15 minute pause between injections to allow for complete contrast clearance. For the second injection, we will infuse up to 1.5 ml of Definity mixed in 25 ml of saline over 5 minutes and then perform subharmonic destruction/reperfusion SHI imaging in multiple imaging planes covering the adnexal mass through the entire period of enhancement (in practice 3-4 minutes of equilibrium contrast concentration); similar to our previous work [Linden et al. 2007; Shi et al. 2001]. The digital clip(s) obtained from the SHI injection will be transferred to a PC for off-line analysis. The SHI images will be qualitatively analyzed as described above. It should be noted, that all subjects will be

closely monitored by a physician during the study [FDA Alert 2007; 2008].

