6.4 Efficacy Assessments

The pre- and then post-contrast ultrasound imaging will be evaluated for each patient as follows: grayscale, grayscale and PDI (baseline), and grayscale and SHI. While this may introduced some bias from pre- to post-contrast results, we considered this the more realistic approach to how CEUS may be used in clinical practice. Each case will be read independently by the 2 experienced co-investigators (15+ years of expertise in CEUS imaging) blinded to the surgical results and contrast-enhanced MRI evaluations, to allow repeatability to be assessed. All ultrasound studies will be rated on a quasi-continuous scale from 0 to 100 ranging from “no lesion seen (no findings)” over “definitely benign,” “indeterminate” to “definitely malignant.” Using a quasi-continuous 100-point rating scale has an intuitive probabilistic interpretation and is known to improve the assessment of the capabilities of the imaging modes studied [Wagner et al. 2001]. The SHI clips will be processed to produce CMI-SHI images [Dave & Forsberg 2009; Dave et al 2010], which will also be read by the blinded readers. Finally, sensitivity, specificity and accuracy will be calculated for all imaging modalities (baseline and SHI as well as MRI) and compared to the RMI values used to select patients for surgery [Ferrazzi et al. 1997; 2005; Moolthiya & Yuenyao 2009].

Off-line SHI TICs will be created on a pixel by pixel basis. Parametric images will be generated showing time-to-peak, perfusion rate, peak intensity (calculated in dB as the ratio of the peak to the baseline values) and area under the curve (AUC) in the area of greatest vascularity as well as parameters across the mass (based on the data from second infusion) [Eisenbrey et al. 2011b]. The TIC parameters will be compared to the lesion characterization of the other imaging modalities with pathology as the reference standard. It is our hypothesis that these new SHI based biomarkers will improve our capabilities to characterize ovarian cancers. Results will also be compared to MRI enhancement kinetics and imaging assessments obtained as part of the subjects’ standard of care.

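### Section 6.2 lets the operator adjust the Definity infusion rate (4-10 ml/min) to visible enhancement, while other sections infuse over 5 minutes; no rule shown holds, records or accounts for the rate behind the across-mass intensity parameters

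*Combined protocol and SAP*

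**What the plan says.** The combined protocol and SAP describes the second contrast administration in four places.

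- Synopsis, Trial Procedures: "Definity will be infused over 5 minutes".
- Section 5, Medications, and again section 6.3.2, Ultrasound Imaging: "infuse up to 1.5 ml of Definity mixed in 25 ml of saline over 5 minutes".
- Section 6.2, Treatment Administration: one vial is used for the bag and is given "at a rate sufficient to provide diagnostic intra-tumoral contrast visibility". The rule for the operator is that "the infusion rate will be maintained within this range but will be adjusted to provide diagnostic intra-tumoral contrast visibility". The range itself comes from the manufacturer, who is cited for the statement that "the infusion rate may vary between 4 ml/min to 10 ml/min".

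Section 6.3.2 performs destruction/reperfusion imaging in several planes during this infusion and expects "in practice 3-4 minutes of equilibrium contrast concentration". Section 6.4, Efficacy Assessments, derives parametric images of four quantities. Three are curve area, perfusion rate and time-to-peak; the fourth is "peak intensity (calculated in dB as the ratio of the peak to the baseline values". It does this in the most vascular area and also for "parameters across the mass (based on the data from second infusion". The parameters are then compared with the other modalities, with pathology as reference.

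**The concern.** A quantitative enhancement parameter is comparable between women only if contrast delivery is the same or is known. Section 6.2 lets delivery respond to the enhancement being measured: a mass that looks dim may be given a faster rate. Expressing the peak in dB over baseline removes gain and tissue background, but not differences in microbubble delivery.

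Two things are at stake. First, section 2 makes quantitative biomarkers and pilot data for a later study part of the primary objective. Means, standard deviations and cut-offs in dB obtained at mixed rates would not carry over to a study run at one rate. If the rate was not written down at the single imaging visit, they could not be corrected. Second, destruction/reperfusion imaging relies on a steady concentration. A rate change between planes disturbs it, and a fast rate shortens it.

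**Working it through.** **Inputs from the documents.** Bag: 25 ml saline plus up to 1.5 ml Definity = 26.5 ml. Stated duration: 5 min. Permitted rate: 4-10 ml/min. Expected equilibrium: 3-4 min. Sample: 45 women, 15-20 % cancers (section 7.2.3), so about 7 to 9.

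**Step 1: the plan's 5 minutes as a rate.** 26.5 / 5 = 5.3 ml/min, which lies inside the section 6.2 range. For a full bag the two descriptions agree only near this rate.

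**Step 2: what the range allows.** Duration = 26.5 / rate; Definity per minute = (1.5 / 26.5) × rate; shift = 10·log10(rate / 5.3), assuming signal power proportional to rate (not in the documents).

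| Rate (ml/min) | Bag lasts (min) | Definity (ml/min) | Shift v 5.3 (dB) |
|---|---|---|---|
| 4 | 6.6 | 0.23 | -1.2 |
| 5.3 | 5.0 | 0.30 | 0 |
| 6.6 | 4.0 | 0.37 | +0.95 |
| 10 | 2.65 | 0.57 | +2.8 |

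End to end this is 10 / 4 = 2.5-fold, or 10·log10(2.5) = 4.0 dB.

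**Step 3: the equilibrium window.** With no wash-in time at all, a 3-minute window needs a rate of at most 26.5 / 3 = 8.8 ml/min, and a 4-minute window at most 26.5 / 4 = 6.6 ml/min. These limits are generous. If equilibrium is taken to end with the bag (an assumption), 5 minutes of infusion yielding 3-4 minutes of equilibrium implies 1-2 minutes of wash-in. That leaves 4.0 - (1 to 2) = 2-3 min at 6.6 ml/min and 2.65 - (1 to 2) = 0.65-1.65 min at 10 ml/min.

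**Step 4: illustrative effect on results.** Binormal model with ROC area 0.75 at a fixed rate (standardised difference 0.954). Assumed, not in the documents: total SD 2-6 dB, measurement SD 0.5-1 dB, a starting rate of 5.3 ml/min, and a rate raised only as far as needed for the dimmest 10-30 % of masses, up to 10 ml/min (+2.76 dB). Over 24 combinations, with 400,000 simulated masses per group:

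- ROC area: 0.74 to 0.75.
- Benign-malignant mean difference in dB: 0.82 to 0.97 of its fixed-rate value.
- Pooled SD: 0.85 to 0.96 of its fixed-rate value.

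**Step 5: against sampling error.** The Hanley-McNeil standard error of an ROC area of 0.75 is 0.113 (7 v 38), 0.106 (8 v 37) or 0.101 (9 v 36). The standard error of the mean difference with 8 v 37 is SD × √(1/8 + 1/37) = 0.39 SD, and 0.39 / 0.954 = 41 % of the difference itself.

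**Step 6: search for a safeguard.** Section 6.2 bounds the rate but does not fix it. Section 5 logs unused drug and vials, not rate. Section 7.2.2 does not adjust for rate. The data forms and the package insert text are not shown.

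**The case against.** The strongest reply is that there is little real conflict. The rate of 5.3 ml/min lies within 4-10, so 5 minutes may be the nominal infusion and section 6.2 its operating limits, taken from the manufacturer. A slower infusion stopped at 5 minutes also fits the words. This stands in part: the sections can be reconciled, but section 6.2 states the visibility rule twice and permits rates far from 5.3 ml/min.

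Second, H1 and H2 (section 7.2.1) are stated as ROC areas and H3 as a correlation. A shift in ROC area of about 0.01 is invisible beside a standard error of 0.10-0.11. Even the mean-difference compression of up to 18 % is less than half its standard error here. That stands, and it limits the severity. The compression is systematic, however, and the pilot's values are meant to inform a later study.

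Third, ensuring visibility is sensible in a pilot and may help the qualitative reading. This also stands, and the fix keeps it possible.

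Fourth, a rate field may exist on a data form. This cannot be excluded. Nor does section 6.4 say which baseline is used for the infusion curves. Delivery need not cancel under either choice, but the size of the effect depends on it.

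A reader might infer that operators would equalise brightness across masses and so remove the benign-malignant contrast. The text does not support that: it asks for a sufficient rate, which is a floor. A reader might also infer that the rate could follow the diagnosis directly. Imaging precedes surgery, so pathology is not yet known.

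**Conclusion.** The point holds with limited scope. The rate may depend on the enhancement being measured, across-mass intensity parameters come from that infusion, and the text shown has no rule to hold, record or account for the rate. That part, and the 2.65-minute bag at 10 ml/min against a 3-4 minute window, need only the documents and arithmetic. Every dB figure is illustrative and rests on signal power being proportional to rate; the compression figures also rest on assumed SDs and an assumed visibility floor.

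The effect is confined to infusion-derived peak intensity and curve area as pilot data. Bolus parameters are unaffected, time-based parameters are less affected, and ROC areas are likely to change little. The documents do not support a claim that H1 or H2 is invalidated. Nor do they support one that the CD31 comparison is distorted, since it uses fractional vascularity and no effect on that has been shown. Severity is low to moderate.

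**What to change.** In section 6.2:

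- Make 5.3 ml/min (a 5-minute infusion of the full bag) the default for every subject, and hold it constant through all destruction/reperfusion planes.
- If a mass is not visible and the rate must differ, set it once before destruction/reperfusion imaging starts and do not change it afterwards.
- Record the rate and the Definity dose drawn.

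In section 6.4 or 7.2.2, report across-mass peak intensity and curve area with the rate accounted for, and flag subjects not imaged at 5.3 ml/min. Those imaged at the default rate are a subset selected on enhancement, so results in them alone should be labelled as such.

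Two refinements are optional: a cap of 6.6 ml/min, and choosing the rate from the bolus clip already acquired. A rate of 6.6 ml/min may leave less than the planned 3-4 minutes of equilibrium, and any exception still ties delivery to enhancement, which is why recording matters most.

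The cost is a few sentences and two data fields; sample size and maximum dose do not change. The downside is that some weakly enhancing masses will look dimmer during the infusion.

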6.3 Trial Assessments

6.3.1 Medical History

A full demographic profile, known drug allergies or intolerances, and a review of the subject’s medical/surgical history will be recorded. If the woman is of childbearing potential, she will have a urine pregnancy test (the results of which will be made available to the subject prior to study initiation). Emergency services (e.g., a crash cart) will be available within the hospital in case of any acute adverse reactions. Adverse events will be monitored during the entire procedure.

6.3.2 Ultrasound Imaging

The ultrasound examinations will be performed by a qualified sonographer. Procedures and equipment for this trial will be used in accordance with typical clinical procedures. All trial procedures will be conducted in accordance with Good Clinical Practice. A modified Logiq E9 scanner with a [REDACTED] C10-3v EV transducer

(GE Healthcare) operating in SHI mode will be used to obtain subharmonic radiofrequency (RF) data from the adnexal mass within the ovary and/or fallopian tube. Both the experimental machine and software will be labeled as an investigational device with a GE provided label prior to beginning any clinical experiments (21 CFR 812.5).

A baseline grayscale ultrasound scan of the lesion will be obtained and the following criteria assessed: the size, shape, and orientation of the site; echogenicity compared to surrounding tissue. Standard PDI of the mass will also be performed to select the area with the greatest vascularity. The distribution of color signals and the overall color content of the mass will be evaluated by comparing the pattern and amount of color to normal tissue on the contra-lateral side. If uniform, the color will be categorized as less intense, iso-intense or more intense than normal tissues. If non-uniform, the color will be described by location, intensity and distribution. Anastomoses between adjacent vessels will be noted (as 1-2, 3-5 or >5 vessels connecting). The vascular pattern will also be graded as peripheral, radial, spotty or a combination. Digital clips of the two baseline imaging modes will be acquired.

Two contrast injections will be performed. The first injection will involve pulse inversion grayscale EV SHI (in a dual display format utilizing at a transmit frequency of 5.8 MHz and the subharmonic obtained at 2.9 MHz [Eisenbrey et al. 2011a; Sridharan et al. 2015]) of the area of greatest vascularity within the adnexal mass (as established by baseline PDI) followed by IV administration of 1.3 to 1.5 ml of Definity and acquisition of the contrast enhancement covering baseline, wash-in and peak enhancement to complete wash-out (typically 1-2 minutes). There will be a 15 minute pause between injections to allow for complete contrast clearance. For the second injection, we will infuse up to 1.5 ml of Definity mixed in 25 ml of saline over 5 minutes and then perform subharmonic destruction/reperfusion SHI imaging in multiple imaging planes covering the adnexal mass through the entire period of enhancement (in practice 3-4 minutes of equilibrium contrast concentration); similar to our previous work [Linden et al. 2007; Shi et al. 2001]. The digital clip(s) obtained from the SHI injection will be transferred to a PC for off-line analysis. The SHI images will be qualitatively analyzed as described above. It should be noted, that all subjects will be

closely monitored by a physician during the study [FDA Alert 2007; 2008].

6.4 Efficacy Assessments

The pre- and then post-contrast ultrasound imaging will be evaluated for each patient as follows: grayscale, grayscale and PDI (baseline), and grayscale and SHI. While this may introduced some bias from pre- to post-contrast results, we considered this the more realistic approach to how CEUS may be used in clinical practice. Each case will be read independently by the 2 experienced co-investigators (15+ years of expertise in CEUS imaging) blinded to the surgical results and contrast-enhanced MRI evaluations, to allow repeatability to be assessed. All ultrasound studies will be rated on a quasi-continuous scale from 0 to 100 ranging from “no lesion seen (no findings)” over “definitely benign,” “indeterminate” to “definitely malignant.” Using a quasi-continuous 100-point rating scale has an intuitive probabilistic interpretation and is known to improve the assessment of the capabilities of the imaging modes studied [Wagner et al. 2001]. The SHI clips will be processed to produce CMI-SHI images [Dave & Forsberg 2009; Dave et al 2010], which will also be read by the blinded readers. Finally, sensitivity, specificity and accuracy will be calculated for all imaging modalities (baseline and SHI as well as MRI) and compared to the RMI values used to select patients for surgery [Ferrazzi et al. 1997; 2005; Moolthiya & Yuenyao 2009].

Off-line SHI TICs will be created on a pixel by pixel basis. Parametric images will be generated showing time-to-peak, perfusion rate, peak intensity (calculated in dB as the ratio of the peak to the baseline values) and area under the curve (AUC) in the area of greatest vascularity as well as parameters across the mass (based on the data from second infusion) [Eisenbrey et al. 2011b]. The TIC parameters will be compared to the lesion characterization of the other imaging modalities with pathology as the reference standard. It is our hypothesis that these new SHI based biomarkers will improve our capabilities to characterize ovarian cancers. Results will also be compared to MRI enhancement kinetics and imaging assessments obtained as part of the subjects’ standard of care.

[name] will mark the transaxial plane of the lesion by sutures upon excision of the adnexal mass, so the specimen can be serially sectioned in the transaxial plane and immunohistochemical staining performed to determine the following variables: tumor type (benign or malignant); if malignant is the cancer invasive or a tumor of low metastatic potential; histological lesion type (epithelial, stromal or germ cell), RMI as well as staging and other markers will be collected as part of the patient's clinical care and correlated with the imaging results. Finally, the ability of EV SHI to image angiogenesis (specifically fractional tumor vascularity) will be compared to so called "hot spots" within surgical specimens stained for an immunohistochemical predictor of angiogenesis, specifically a monoclonal antibody against the CD31 endothelial cell marker (Dako Corporation, Carpinteria, CA). The principal investigator of this project has, as part of previously NIH and DOD funded projects, developed the necessary software for quantitative analysis of CEUS images and specimens stained with CD31 using a histomorphometry system based on an Labophot-2 microscope (Nikon, Melville, NY) and ImagePro Plus software [Forsberg et al. 2008].

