3. TRIAL DESIGN

This is an open-label, non-randomized pilot study that will be conducted at one clinical site, Thomas Jefferson University (TJU). Enrolled patients scheduled for subsequent surgery of an adnexal mass will receive a bolus IV injection followed 30 minutes later by a continuous infusion of the ultrasound contrast agent Definity. Contrast ultrasound imaging will be performed using an EPIQ scanner with a broad

bandwidth C10-3v EV transducer operating in SHI mode. Results will be compared to MRI assessments and pathology obtained as part of the subjects' standard of care.

A full demographic profile, known drug allergies or intolerances, and review of the subject's medical/surgical history will be recorded. If the subject is of childbearing potential, she will have a urine pregnancy test (the results of which will be made available to the woman prior to study initiation).

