4.1 Inclusion Criteria

All subjects accepted for this trial must fulfill all the following criteria:

- Be diagnosed with an adnexal mass.
- Be scheduled for surgery to remove the adnexal mass.
- Be at least 21 years of age.
- Be clinically stable.
- If a female of child-bearing potential, must have a negative pregnancy test.
- Be conscious and able to comply with study procedures.
- Have read and signed the IRB-approved Informed Consent form for participating in the study.

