7.2.2 Analysis of Results

The findings of SHI will be correlated to vascular morphology (i.e., tumor angiogenesis ascertained with CD31) and other imaging and pathological findings; including size, vascularity, presence or absence of receptors and RMI values. The techniques will be compared using an analysis of variance (ANOVA) with method (i.e., baseline ultrasound imaging, SHI, or MRI) as the dependent variable and outcome as the independent variables. For the pre and post-contrast enhanced comparisons, dichotomous parameters (e.g., benign/malignant) and ranked data (less, iso, or more intense) will be analyzed with the McNemar test. The ability of the imaging tests to distinguish benign from malignant masses will be compared using ROC analysis, while the incremental validity of imaging diagnosis and morphological characteristics as well as serum biomarkers (i.e., RMI) will be analyzed using logistic regression and ROC analyses [DeLong et al. 1988; Metz 1986; Wagner et al. 2001]. Differences between ROC curves will be tested by computing Mann-Whitney statistics. All of the statistical analyses proposed for this human clinical trial will be repeated split by racial and ethnic groups to determine if clinically important race/ethnicity differences exist in the ability of SHI to characterize adnexal masses (although the limited sample size of this pilot study makes it unlikely that such differences – if any exist - will be detectable).

All analyses and computations will be performed using NCSS/PASS 2008 and Stata 12.0 (Stata Corporation, College Station, TX), while the study database will be designed and implemented in REDCap (Vanderbilt University, Nashville, TN). This database will contain all patient information (except names and other identifiers), including pathology, MRI and SHI measurements as well as other clinical variables.

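### SHI is scored 0-100 by blinded readers while MRI is an unscaled standard-of-care result not required for entry, so the planned SHI-v-MRI ROC comparison mixes scales and possibly women; the fix is one common scale and women with both tests.

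*Combined protocol and SAP*

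**What the plan says.** **Ultrasound.** Section 6.4 states: "All ultrasound studies will be rated on a quasi-continuous scale from 0 to 100". The scale runs from no lesion seen, through definitely benign and indeterminate, to definitely malignant. Two co-investigators read each case independently, blinded to surgery and to MRI. The section adds that such a scale "is known to improve the assessment of the capabilities of the imaging modes studied".

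**MRI.** Section 3 says: "Results will be compared to MRI assessments and pathology obtained as part of the" subjects' standard of care. Section 6.4 repeats this: "Results will also be compared to MRI enhancement kinetics and imaging assessments obtained as part of the" same routine care. No study reader, rating scale, number of categories, positivity threshold or blinding is given for MRI.

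**Who has an MRI.** Section 4.1 asks that a woman "Be scheduled for surgery to remove the adnexal mass"; no criterion asks for an MRI. Section 6.7.1 defines completion by the two contrast administrations and the ultrasound study alone. No rule covers women without an MRI.

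**Analysis.** Section 6.4: "sensitivity, specificity and accuracy will be calculated for all imaging modalities (baseline and SHI as well as MRI", with no denominators stated. Section 7.2.2: "The ability of the imaging tests to distinguish benign from malignant masses will be compared using ROC analysis", and "Differences between ROC curves will be tested by computing Mann-Whitney statistics". The same section lists baseline ultrasound, SHI and MRI as the methods compared. H2 in section 7.2.1 names contrast-enhanced MRI as a comparator and sets an SHI AUC of at least 0.75 against comparator values of 0.70 to 0.72.

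**The concern.** The Mann-Whitney statistic is the empirical AUC. Each benign-malignant pair with the same score counts one half. A test reported in few categories has many such ties, so its empirical AUC falls below that of the same test read on a fine scale. Two equally good tests, one scored 0-100 and the other reported in a few categories, would therefore show a difference in favour of the finely scored one.

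The second problem is the set of women. If some have no MRI, the plan does not prevent SHI sensitivity and specificity being computed on all women and the MRI figures on those who happened to be scanned. The two sets of figures could then describe different case mixes.

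The estimate for the next study is at stake. Section 7.2.3 says the pilot is meant to supply data for a larger trial. A confidence interval shows sampling noise. It does not show a scoring artefact, which would pass into the assumed effect size.

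**Working it through.** **The plan's own precision figure.** Section 7.2.3 gives only one: r = 0.70, n = 45, 95% CI (0.51, 0.82). By Fisher's z, tanh(atanh 0.70 ± 1.96/√42) = (0.512, 0.824), so it reproduces. No precision is stated for any AUC or AUC difference.

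**Inputs.** From 7.2.1: SHI AUC 0.75 and comparators 0.70-0.72, so the implied gap is 0.75 − 0.72 = 0.03 to 0.75 − 0.70 = 0.05. From 7.2.3: 45 women, 15-20% cancers, which is 6.75 to 9, or about 7-9. Assumed: an equal-variance binormal model and, because the documents are silent, a range of MRI category counts.

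**Separation.** d = √2 × z(0.75) = 1.414 × 0.6745 = 0.954.

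**Two categories, best cut at d/2.** AUC = Φ(d/2) = Φ(0.477) = 0.683. Loss 0.750 − 0.683 = 0.067.

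**Three categories, cuts at d/2 ± 0.5 = −0.023 and 0.977.** Benign women fall 0.491, 0.345, 0.164 across the categories; malignant cases fall 0.164, 0.345, 0.491. Then AUC = 0.164 × (0.491/2) + 0.345 × (0.491 + 0.345/2) + 0.491 × (0.836 + 0.164/2) = 0.040 + 0.229 + 0.451 = 0.720. Loss 0.030.

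**Loss of empirical AUC by number of categories, cut points at their best:**

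| True AUC | 2 | 3 | 4 | 5 | 7 |
|---|---|---|---|---|---|
| 0.70 | 0.055 | 0.026 | 0.015 | 0.010 | 0.005 |
| 0.72 | 0.060 | 0.028 | 0.016 | 0.010 | 0.005 |
| 0.75 | 0.067 | 0.030 | 0.017 | 0.011 | 0.006 |
| 0.80 | 0.076 | 0.034 | 0.019 | 0.012 | 0.006 |
| 0.90 | 0.082 | 0.035 | 0.019 | 0.012 | 0.006 |

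On a 101-point scale the loss is about 0.0001. At true AUC 0.75, five categories lose 0.011, which is 22% of a 0.05 gap and 37% of a 0.03 gap.

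**Cut points away from the best lose more.** For a binary call at specificity 0.90, sensitivity is Φ(0.954 − 1.282) = 0.372 and AUC = (0.90 + 0.372)/2 = 0.636, a loss of 0.114.

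**Sampling error.** Hanley-McNeil with A = 0.75, Q1 = A/(2 − A) = 0.600, Q2 = 2A²/(1 + A) = 0.643:
- 7 cancers, 38 benign: √[(0.1875 + 6 × 0.0375 + 37 × 0.0804)/266] = 0.113.
- 9 cancers, 36 benign: √[(0.1875 + 8 × 0.0375 + 35 × 0.0804)/324] = 0.101.

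With an assumed correlation of 0.5 between the two AUCs, the SE of the paired difference is about 0.10-0.12. Power for a gap of 0.03-0.05 is about 6-8% (two-sided 0.05, assumed). A smaller MRI subset makes both worse.

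**The case against.** - **The category count is unknown.** This stands. A reader might infer that the comparison is biased towards SHI by the size of the H2 effect. The documents do not support that as a flat statement. It holds for two categories, is borderline for three (0.026-0.028 at true AUC 0.70-0.72, just under the smallest gap), and fails for five or more.
- **The net direction is not established.** This stands. Blinding is stated only for the ultrasound readers, and a routine MRI report may draw on clinical information that helps MRI. Which women have an MRI could push the result either way. A reader might infer a net tilt to SHI; only the scale effect, other things equal, has that sign.
- **The H2 benchmark is loose.** This stands. The 0.70-0.72 is a low-end accuracy, not an MRI AUC, so 0.03-0.05 is an implied yardstick. The SHI end-point of 0.75 does not depend on how MRI is scored.
- **The plan speaks of better assessment, not higher scores.** This is correct. The scale sentence does not admit inflation; it shows only that the chosen advantage was not extended to MRI.
- **MRI is not confined to a coarse call.** Section 6.4 also mentions enhancement kinetics, and its sensitivity and specificity already require a binary call. But the plan turns neither into an ROC score, and it gives no threshold. The binary requirement makes a two-level MRI variable plausible.
- **It is a pilot, and noise exceeds the artefact.** This is true and limits the consequence. It does not excuse an avoidable artefact in a figure meant to be carried forward.

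**Conclusion.** The point holds in conditional form. As written, the plan compares tests on unequal scales and possibly on different women. With true AUC 0.75, coarseness alone lowers the empirical MRI AUC by about 0.07 in two categories, 0.03 in three and 0.01 in five, against an implied H2 gap of 0.03-0.05. This rests on the equal-variance binormal model, near-optimal cut points and an assumed number of MRI categories.

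The missing MRI requirement leaves the paired sample undefined; its effect on direction is unknown. Because the SE of the difference is about 0.10-0.12, the artefact would not decide this trial's result. It would distort the pilot estimate handed to the next study. The remedy is cheap enough that the plan should be changed.

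**What to change.** In sections 6.4 and 7.2.2:

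1. Restrict every SHI-v-MRI figure, including sensitivity, specificity and accuracy, to women with both tests. Report how many they are and how many have cancer.
2. State how an MRI report becomes a score. For SHI v MRI, map the 0-100 rating to the categories of the MRI report. Set the cut points before unblinding to pathology, with a written rule for indeterminate results and for the no-lesion end of the scale. On that common scale, give paired sensitivity and specificity with exact confidence intervals, or DeLong AUCs.
3. Treat McNemar as descriptive. With 7-9 cancers, an exact two-sided test on sensitivity needs at least six discordant pairs, all in one direction (2 × 0.5⁶ = 0.031; five give 0.0625).
4. Keep the 0-100 AUC for comparisons among ultrasound modes and for the SHI end-point of 0.75.
5. Record whether the MRI reports were made with knowledge of other clinical findings. Steps 1-4 do not correct for that.

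**Cost:** a few lines of text, with no extra scan or reader. The downsides are a smaller paired sample, some information lost by collapsing the scale, and a somewhat lower SHI AUC in the MRI comparison. A blinded MRI re-read on the 0-100 scale would also remove the scale mismatch, but it costs reader time and is not needed.
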